In particular, antioxidant supplements are a promising area of research in the prevention and treatment of CVD. Observational data have identified associations between intake of carotenoids, folic acid, and vitamin E and CVD risk (Lichtenstein, 2009). Research shows that antioxidants have the ability to inhibit the oxidation of cholesterol and improve endothelial function (Malekmohammad, Sewell, & Rafieian-Kopaei, 2019). High antioxidant intake has been shown to prevent atherosclerosis (Nunez-Cordoba & Martinez-Gonzalez, 2011).

Despite biological plausibility about the effects of antioxidants to reduce CVD risks as suggested with some observational studies, data derived from most nutrient supplement trials have been disappointing (Monsen, 2000). The discrepancies between observational and interventional data may be due to confounding diet and lifestyle patterns and unaccounted for genotypic variations. It may also be that specific nutrients need to be given together to translate into significant changes. Specific nutrients working in concert may produce a health benefit greater than the sum of the individual parts. For example, human studies have shown convincingly the dose-dependent enhancing effects of ascorbic acid (vitamin C) on iron absorption (Lynch & Cook, 1980). Whether it is because they enhance each other's absorption or because they have more potent physiological effects when taken together, pairing nutrients that have a synergistic effect may lead to more favourable outcomes. It may be that combinations of nutrient supplements need to be given together to translate into significant changes.

Although direct comparisons between multi-ingredient supplements and single ingredients have never been done, a substantial body of evidence suggests that multi-ingredient formulations greatly increase the efficacy of the product (Harty et al., 2018). For example, there is research to suggest that multi-ingredient supplements can improve lipid blood profiles in as little as 30 days (Hobbs, Caso, McMahon, & Nymark, 2014). However, the body of literature evaluating dietary supplements to reduce CVD prevalence and prognosis is minimal. The view by most health care practitioners and government agencies is that currently there is insufficient data to recommend the routine use of nutrient supplements to prevent or treat CVD. It is only in the last decade that dietary supplement databases with open access for the public have existed in the USA (Coates, 2016). Although a great deal of progress has been made in recent years, much remains to be done to ensure that dietary supplements are safe, efficacious, and reasonable in cost

so that they contribute positively to the public's health. Given the potential benefit of these products, more research needs to be done.

Cardioflex is a multi-ingredient supplement comprised of amino acids (L-lysine, L-proline, L-glutamine, L-threonine), vitamins (vitamins A, C, E, folate, vitamin B12), minerals (potassium, magnesium, selenium) and CoQ10. The individual ingredients in Cardioflex have shown or been hypothesized to show, positive results in reducing CVD and CVD risk factors. For example, the literature demonstrates that amino acids can play a significant role in cardiovascular health. L-threonine supplementation has been shown to lower blood pressure in patients with CVD (Tuttle, Milton, Packard, Shuler, & Short, 2012). High antioxidant intake has been shown to prevent atherosclerosis (Nunez-Cordoba & Martinez-Gonzalez, 2011). Low blood serum levels of magnesium have been associated with an increased risk for several chronic diseases including diabetes, hypertension, coronary heart disease, and osteoporosis (Kass, Weekes, & Carpenter, 2012). Multiple randomized, placebo-controlled, clinical trials show that daily supplementation of CoQ10 can cause significant antihypertensive effects in as little as 4 weeks of treatment (Ho, Bellusci, & Wright, 2009).

This clinical trial will help clarify the role of multi-ingredient supplements containing amino acids, vitamins, and minerals in the prevention and management of CVD and CVD risk factors.

RESEARCH OBJECTIVES

The overall objective of this study is to determine whether daily supplementation with the dietary supplement Cardioflex for 90 days will reduce risk factor biomarkers for CVD in adults aged 30–65 years old.

The primary objective is to determine whether daily supplementation with the dietary supplement Cardioflex will improve their plasma lipid profile (total cholesterol, HDL-cholesterol, LDL-cholesterol, triglycerides, lipoprotein A).

The secondary objectives are to determine if Cardioflex supplementation will improve anthropometric measures (waist circumference, body mass index), cardiac measures (heart rate, heart rate variability, accelerated plethysmography (APG age, which measures the biological age of arteries), blood pressure), and inflammatory and endothelial function biomarkers (C-reactive protein, IL-6, sICAM-1, sVCAM-1,) and assess the safety of the supplement by measuring serum levels of liver and kidney enzymes (alanine transaminase; ALT, aspartate transaminase; AST, lactate dehydrogenase; LHD, blood urea nitrogen; BUN, and creatinine). To quantify confounding variables, participants were asked to record everything they ate and drank in a food log and wore a pedometer to

track total steps on day 1 (beginning), day 45 (mid-point) and day 90 (end) of the study.

HYPOTHESES

- Participants who consume one serving (10 g) of Cardioflex per day, the label recommended dosage, will have improved lipid profile, as reflected by lower levels of total cholesterol, LDL-cholesterol, triglycerides, and lipoprotein A, and higher HDL-cholesterol than participants who consumed the placebo.
- Participants who consume one serving of Cardioflex per day will have improved cardiac health, as measured by lower blood pressure, higher HRV, lower APG age, and lower levels of inflammation biomarkers (C-reactive protein, IL-6, sICAM-1, and sVCAM-1) than participants who consumed the placebo.
- No significant changes will be seen in anthropometric measures (waist circumference, body mass index) or liver and kidney functions biomarkers (ALT, AST, LHD, BUN or creatinine) between the Cardioflex and the placebo group.

STUDY DESIGN

This was a randomized, double-blind, placebo-controlled, parallel design study where participants were assigned to receive one serving (10g) of Cardioflex or 10g of a maltodextrin placebo daily for 90 days and independent of any other diet or exercise interventions. The study was conducted at the Richardson Centre for Functional Foods and Nutraceuticals (RCFFN), located at the University of Manitoba Ft. Garry Campus. The study was registered on clinicaltrials.gov with ID number NCT03826914 and approved by the University of Manitoba Joint-Faculty Research Ethics Board (JFREB) with protocol number J2018:010 (HS21609).

The current lack of accepted guideline recommendations for nutrient supplements is explained by the lack of clinical evidence showing nutrient therapy's effectiveness and safety. Hence, a placebo-controlled randomized clinical trial is warranted. Randomly assigning the intervention eliminates the influence of unknown confounding variables or bias that could lead to an incorrect measurement of treatment effect. Randomization eliminates confounding baseline variables, thus eliminating the possibility that the observed effects are because one treatment group had a more advantageous starting point. The placebo control allows participants, investigators, and study staff to be blinded. The advantage of a placebo-controlled trial over an observational study is the ability to demonstrate causality.

Participants were given the treatments as individual stick packs so there was no variance in the daily dosage consumed. Participants were told to mix the supplement with water

and consume it before eating breakfast daily. The group supplementing with Cardioflex ingested one serving (10g) of Cardioflex daily, whereas the placebo group ingested 10g of maltodextrin placebo. We chose this as our placebo supplement because it was likely to have minimal effect on CVD health biomarkers. A log was given to the participants to record their supplement intake. Compliance with the supplement protocol was assessed by measuring blood levels of CoQ10 and providing participants with more treatment packages than the total number of days of the study and asking the participants to return any unused stick packs to the supplement coordinator at the end of the study. We chose blood levels of CoQ10 as our main indicator of compliance because it is not readily found in food and previous research found a significant increase in plasma CoQ10 concentrations when participants were given Coq10 supplements daily (Niklowitz, Sonnenschein, Janetzky, Andler, & Menke, 2007). Thus, it is anticipated that a participant's CoQ10 blood values should increase with Cardioflex supplementation and would indicate compliance with taking the supplement. In addition, participants were given a randomized number of stick packs between 93 and 100, giving every participant at least a few stick packs to return at the end of the clinical trial. Participants were not told the number of stick packs they were given.

Participants were instructed to follow the same diet and maintain the same level of physical activity throughout the clinical trial. To assess dietary intake and physical activity, participants were asked to record everything they ate and drank in a food log and wore a pedometer to track total steps on day 1 (beginning), day 45 (mid-point) and day 90 (end) of the study. A 90-day study length was chosen because previously published data saw significant changes in triglycerides, LDL-cholesterol, HDL-cholesterol, and total cholesterol when participants were given a multi-ingredient supplement for 90 days (Lombardo et al., 2013). A sample size calculation was completed using previously published data (Hobbs et al., 2014) to ensure enough participants were recruited. We calculated that we would need 60 subjects to reach statistical significance. With an expected attrition rate of 20%, we determined that 72 participants needed to be recruited.

To determine the effects of Cardioflex on CVD risk, the dependent variables tested included anthropometrics (weight, height, waist circumference), cardiovascular parameters (blood pressure, heart rate, HRV, APG age), dietary intake, plasma lipid profile (total cholesterol, HDL-cholesterol, LDL-cholesterol, triglycerides, lipoprotein A), and inflammatory and endothelial function biomarkers (C-reactive protein, IL-6, sICAM-1, sVCAM-1). Anthropometrics were included because large scale epidemiological studies have shown correlations between CVD mortality and BMI (Valavanis, Mougiakakou, Grimaldi, & Nikita, 2010) and increased waist circumference is recognized as a major cardiometabolic risk factor (Tchernof & Despres, 2013). Cardiovascular parameters carry valuable information for the prediction of long-term and near-term CVD risk. Blood

pressure is a consistent risk factor for the development of atherosclerosis (Lu, Cassis, & Daugherty, 2007). A higher resting heart rate is linked with greater CVD risk (Fox et al., 2007). Reduced HRV is associated with an increased risk for coronary heart disease and CVD mortality (Liao et al., 1997). Arterial elasticity is an established risk factor to predict future CVD events (Glasser et al., 1997). Lipid profile is recognized as an established risk factor in the development and progression of CVD (Graham, Cooney, Bradley, Dudina, & Reiner, 2012; Jellinger et al., 2012). Inflammation and endothelial function play a significant role in developing atherosclerosis, and risk of future cardiovascular events (Jarvisalo, Juonala, & Raitakari, 2006).

PARTICIPANTS

Recruitment of study participants employed several strategies including email, flyers, and in-person presentations. The study eligibility criteria were adult men and women between the age of 30-65 years old, perform less than 150 minutes of moderate or vigorous physical activity per week, have not used prescription cholesterol or blood pressure medication in the last 3 months, be willing to stop taking any dietary supplements during the study period of 90 days, not pregnant nor planning on getting pregnant during the study, and an APG type of D, E, F or G and/or an HDL-cholesterol to total cholesterol ratio of ≤ 24 percent.

Participants were stratified (male/female) and randomized (block size = 5) to the study treatments using a computer-generated randomization (www.randomizer.org) numbering system.

SAMPLE SIZE

A sample size calculation was completed using a standard sample size in equation 1 to determine the number of participants needed for the study. With $\alpha = .05$ and $\beta = .90$ and a 12% mean decrease of cholesterol using previously published data (Hobbs et al., 2014) in the supplementation group, we calculated that we would need 60 subjects to reach statistical significance. With an expected attrition rate of 20%, we determined that 72 participants needed to be recruited.

$$n = \frac{2(Z_{\alpha} + Z_{1-\beta})^2 \sigma^2}{\Delta^2}$$

Equation 1 - Estimated sample size equation

Z_{α} = constant to the accepted error, $Z_{1-\beta}$ = constant according to power, σ = standard deviation, Δ = effect size

Overall, 90 adults were screened for eligibility, with 75 adults being deemed eligible. At the time of starting the study 69 adults chose to participate, and 6 eligible adults chose not to participate for personal reasons not related to the study.

STUDY PROCEDURES AND ASSESSMENTS

BLOOD COLLECTION

Blood was drawn at 3 time points in the study – the assessment for eligibility for entry into the study, baseline, and end of the 90-day supplement period. All blood samples were collected in the morning after at least 8 hours overnight fast. The participants reported to the RCFFN at the University of Manitoba Ft. Garry Campus. Blood samples were taken by venipuncture from an antecubital vein into serum tubes by a certified phlebotomist. For eligibility assessment, one 5mL serum tube was withdrawn. For clinical trial baseline and endpoint measurements, two 10mL serum tubes, and one 5mL serum tube, totaling 25mL of blood was withdrawn from each participant. Samples were centrifuged at 4100g for 10 minutes. The plasma was allocated into Eppendorf tubes and frozen at -86 ° C for later analysis.

Cardiac Measurements

Participants were required to sit for a minimum of 5 minutes rest at the beginning of each assessment session. Blood pressure was measured at the brachial artery of the left arm, using an automatic sphygmomanometer (Series 10, Omron). The blood pressure of each participant was taken three times, and the average was recorded. Accelerated plethysmograph (APG) type, HR, and HRV were assessed using a Meridian digital pulse-wave analyzer (DPA) machine (Long Life Cardio LLC, USA). HRV was measured using the standard deviation of all of the RR intervals (the distance between each heartbeat) after 5 minutes of recording.

ANTHROPOMETRICS

All anthropometric measurements were collected with minimal clothing, without shoes and all metals removed from the body. Height in cm was measured using a standard stadiometer, body mass was measured using a digital scale (7562EF, Taylor Precision Products, USA). BMI calculation was performed by dividing weight in kg by height in meters squared (kg/m^2). Waist circumference was measured at the level of the iliac crest with the participants in a standing position.

Dietary Intake Records and Analysis

Detailed dietary data and total steps were collected from the participants on 3 occasions; that is, data was collected on day 1 (beginning), day 45 (mid-point) and day 90 (end) of the study using a 1-day food record method to determine participants' intake of all food, and drink, and a pedometer to track daily total steps. Participants recorded all details of food and drink type, method of preparation, and estimated portions. A 1-day food record was chosen to minimize respondent burden. Food and activity records were collected from participants during the final assessment session.

Basal metabolic rate (BMR) was calculated by Equation 2 for input into Goldberg's energy cut-off equation. The Goldberg's energy cut-off equation (Black, 2000) with a perceived activity level of 1.5 and 95% confidence interval was used to remove outliers who provided diet records of poor validity. Three outliers were removed from the dietary analysis; one in the Cardioflex group and two in the placebo group.

$$\text{Men: BMR} = 88.362 + (13.397 \times \text{weight in kg}) + (4.799 \times \text{height in cm}) - (5.677 \times \text{age in years})$$

$$\text{Women: BMR} = 447.593 + (9.247 \times \text{weight in kg}) + (3.098 \times \text{height in cm}) - (4.330 \times \text{age in years})$$

Equation 2 – Basal metabolic rate calculation*

*Information adapted from (Harris & Benedict, 1918)

Dietary records were analysed for differences in energy intake, protein, carbohydrate, fat, and micronutrients among treatments. Dietary analysis was completed by inputting all food record data into Food Processor Nutrition Analysis Software V11.7 (ESHA Research, USA).

BLOOD ANALYSIS

Serum concentrations of total cholesterol, triglycerides, HDL-cholesterol, BUN, creatinine, AST, ALT, and LDH were measured using automated enzymatic methods on a Vitros-350 chemistry analyzer. LDL-cholesterol levels were estimated using the Friedewald formula: $\text{LDL-cholesterol} = \text{Total cholesterol} - \text{HDL-cholesterol} - \text{triglycerides}/2.2$ (Rifai N, 2006).

CRP, IL-6, SiCAM, and SvCAM were measured using Meso Scale Discovery V-PLEX assays (MSD, Rockville, Md., USA). 25 μL of sample, calibrator, or control was added to each well of a 96-well plate. The calibrator and control were provided by Meso Scale Discovery. The plate was sealed and incubated at room temperature for 2 hours on a plate shaker set to 400 rpm. Next, 25 μL of detection antibody was added to each well. The plate was sealed and incubated for 1 hour at room temperature on a plate shaker set to 400 rpm. Finally,

150 μL of read buffer was added to each plate and the plates were read on the Meso Scale Discovery QuikPlex SQ 120 instrument. All blood analysis was done in duplicates, with the average of the two values being recorded.

Lipoprotein A was measured using ELISA assay (Human lipoprotein A No.ab212165, Abcam Trading Company, Ltd, China). 50 μL of sample or standard and 50 μL of antibody were added to each well of a 96-well plate. The plate was incubated at room temperature for 1 hour on a plate shaker set to 400 rpm. Next, 100 μL of TMB substrate was added to each well, followed by incubating the plate for 10 minutes on a plate shaker set to 400 rpm. Finally, 100 μL of stop solution was added to each well and the plate was read with a microplate reader set to 450 nm (autoreader EL311; Bio-tek instruments). All blood analysis was done in duplicates, with the average of the two values being recorded.

Coenzyme Q10 was measured using ELISA assay (Human CoQ10 No. CSB- E14081h, Cusabio® Biotech Co., Ltd, China). 50 μL of sample or standard and 50 of HRP-conjugate was added to each well of a 96 well plate. The plate incubated for 40 minutes at 37°C. Next, 90 μL of TMB substrate was added to each well. The plate incubated for 20 minutes at 37°C. Finally, 50 μL of stop solution was added to each well, and the plate was read with a microplate reader set to 450 nm (autoreader EL311; Bio-tek instruments). The blood analysis was done in duplicates, with the average of the two values being recorded.

STATISTICAL ANALYSIS

Data were analyzed using IBM SPSS Statistics (v.25). Significance was determined using the treatment effect between groups. The significance value was set at $p \leq 0.05$. An independent t-test showed that there were no statistical differences between the starting points of the two groups ($P > 0.05$), indicating that the two groups were indistinguishable from each other.

The primary analysis was conducted using the post-treatment biomarker value, comparing the two groups, and controlling for their baseline values by using analysis of covariance. Analysis of covariance examines the differences in the mean values of the dependent variable that is related to the effect of the controlled independent variable while taking into account the influence of the uncontrolled variables. In this study, the dependent variable was the biomarkers being tested, the controlled independent variable was the treatment given and the uncontrolled variables were the baseline differences between participants. Analysis of covariance makes the assumption that the data is normally distributed in equal variances. To check the assumption of normal distribution, a Shapiro–Wilk test was performed. To check the assumption of equal variance, a Levene's test was performed.

Results are given as mean \pm standard deviation (SD). Outliers were determined as values greater or less than the mean \pm 3*SD (Jones, 2019). If outliers were present, they were removed, and the results were recalculated. For each parameter, the percent change was calculated by equation 3.

$$\% \text{ Change} = \frac{\text{Final Value} - \text{Starting Value}}{\text{Starting Value}} \times 100$$

Equation 3: Percent change calculation

REFERENCES

- Benjamin, E. J., Muntner, P., Alonso, A., Bittencourt, M. S., Callaway, C. W., Carson, A. P., . . . Stroke Statistics, S. (2019). Heart Disease and Stroke Statistics-2019 Update: A Report From the American Heart Association. *Circulation, 139*(10), e56-e528. doi:10.1161/CIR.0000000000000659
- Black, A. E. (2000). Critical evaluation of energy intake using the Goldberg cut-off for energy intake:basal metabolic rate. A practical guide to its calculation, use and limitations. *Int J Obes Relat Metab Disord, 24*(9), 1119-1130. doi:10.1038/sj.ijo.0801376
- Canada, S. (2020). Table 13-10-0801-01 Leading causes of death, total population. Retrieved from <https://www150.statcan.gc.ca/t1/tb11/en/tv.action?pid=1310080101>

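### The primary objective covers five lipids with no success rule, no stated sidedness and no multiplicity adjustment; if any one lipid suffices and tests are two-sided, false-benefit risk is about 9–11%, against 2.5% for one test

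*Combined protocol and SAP*

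**What the plan says.** All places are in the combined protocol and SAP.

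- **Research Objectives.** One primary objective spans five measures: the supplement "will improve their plasma lipid profile (total cholesterol, HDL-cholesterol, LDL-cholesterol, triglycerides, lipoprotein A").
- **Hypotheses.** Participants on the supplement "will have improved lipid profile, as reflected by lower levels of total cholesterol, LDL-cholesterol, triglycerides, and lipoprotein A, and higher HDL-cholesterol", compared with placebo. This gives a direction for each lipid and joins them with *and*. It does not say how many must reach significance.
- **Statistical Analysis.** "The primary analysis was conducted using the post-treatment biomarker value, comparing the two groups", with adjustment for baseline by ANCOVA. The outcome is generic: "In this study, the dependent variable was the biomarkers being tested". "The significance value was set at" p ≤ 0.05. The section contains no primary lipid, testing order, composite, success rule, statement of sidedness or adjustment for multiple tests.
- **Sample Size.** The calculation uses α = .05, β = .90 "and a 12% mean decrease of cholesterol using previously published data", and concludes: "we calculated that we would need 60 subjects to reach statistical significance". The type of cholesterol is not specified and is not called the primary endpoint. Equation 1 uses Z with subscript α, described only as a "constant to the accepted error", so it does not settle sidedness either.
- **Blood Analysis.** LDL is not measured. It is calculated by Friedewald as total cholesterol minus HDL minus triglycerides/2.2.

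**The concern.** The error rate of the primary claim depends on a decision rule that the plan does not give. Each of five lipids is tested at the full 0.05 level, and a report could present one significant lipid as meeting the primary objective without departing from anything written. The 0.05 level does not hold for that claim. A report that required all five lipids would keep the level. Nothing in the Statistical Analysis section binds the report to either reading. At stake is whether a positive statement about the lipid profile carries the error rate that a reader will attach to p ≤ 0.05.

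**Working it through.** **The plan's own figure.** The plan states no family-wise error rate, so there is none to reproduce. Its 60 subjects cannot be reproduced either, because no SD is given. Equation 1 can be inverted. Reading β = .90 as 90% power, 60 as the total (30 per arm, equal allocation assumed) and α as two-sided:

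- Effect = (1.960 + 1.282) × √(2/30) = 0.837 SD. With a 12% decrease this implies an SD of 12/0.837 ≈ 14.3 percentage points.
- If Z is one-sided: (1.645 + 1.282) × √(2/30) = 0.756 SD, an SD of about 15.9 percentage points.

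**False benefit if any one favourable lipid suffices and none truly changes.**

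- One two-sided test at 0.05: 0.025 in the favourable direction.
- Upper bound under any correlation: 5 × 0.025 = 12.5%.
- Five independent tests: 1 − 0.975⁵ = 11.9%. This is a reference value only, since a calculated LDL cannot be independent of its components.
- Linked lipids, by simulation: 30 per arm, t-tests on normal residuals standing in for ANCOVA, LDL from the Friedewald formula. Favourable means lower total cholesterol, LDL, triglycerides and lipoprotein A, and higher HDL.

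The documents give no correlations or SDs, so these are assumptions. Four correlation sets were crossed with three SD sets, giving 12 scenarios:

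- Correlations (total cholesterol–HDL, total cholesterol–triglycerides, HDL–triglycerides, total cholesterol–lipoprotein A): all zero; 0.1, 0.15, −0.2, 0.05; 0.2, 0.3, −0.35, 0.1; 0.3, 0.45, −0.5, 0.2.
- SDs for total cholesterol/HDL/triglycerides in mmol/L: 0.9/0.3/0.7; 0.5/0.15/0.45; 0.8/0.3/1.0.

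| Rule, no true effect | One test | Five linked lipids | All correlations 0.7 |
|---|---|---|---|
| Any one favourable, two-sided 0.05 | 2.5% | 9.5–10.7% | 7.7% |
| Any one favourable, one-sided 0.05 | 5% | 17.8–20.2% | 13.8% |
| Any one different in either direction, two-sided 0.05 | 5% | 18.3–20.2% | 15.4% |
| Holm, favourable, two-sided family-wise 0.05 | – | 2.1–2.4% | – |

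A separate normal-theory calculation with other assumed SDs and correlations gave 9.0–10.9% for the first row. Hence about 9–11%.

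**If all five are required.** A false claim is almost impossible when nothing changes. When the other four improve and lipoprotein A does not, it stays at about the nominal 2.5% or less (simulated 1.2–2.7%).

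**Power at the first Holm step (0.05/5 = 0.01).** With 30 per arm, 0.837 × √15 = 3.242, and 3.242 − 2.576 = 0.666, giving 74.7% (normal) or 71.7% (t). With 69 enrolled and the planned 20% attrition, 69 × 0.8 ≈ 55 remain: 0.837 × √(27.5/2) = 3.104, and 3.104 − 2.576 = 0.528, giving 70% (normal) or 67% (t). If Equation 1 was one-sided (0.756 SD) and 60 are analysed, 63.7% (normal) or 60.5% (t).

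**The case against.** The strongest reply is that the Hypotheses section already defines improvement conjunctively, with four lipids lower and HDL higher. On that reading there is no inflation, and no passage says that one lipid is enough. This stands in part: a reader might infer that the plan runs at a 9–11% error rate, and the documents do not support that. What they show is an unstated rule, and the inflation follows only if any one lipid is accepted. But a directional hypothesis is not a decision rule, and the analysis section adopts none.

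A reader might also put the risk at 12%. That needs five independent tests, which the calculated LDL rules out.

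The cholesterol used for sizing might be thought to identify the primary lipid. Its type is not specified and it is not designated primary. The trial registration cited under Study Design was not seen and might name one.

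Two cautions about the remedy also stand. First, allowing an unadjusted all-five claim beside Holm could give contradictory statements: with all five p-values at 0.04, Holm stops at 0.01 and no lipid has improved, yet the all-five rule would say the whole profile has. Second, the document is in the past tense and reports completed checks, so a rule written in now could look prespecified when it was not.

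**Conclusion.** The concern holds in conditional form. The plan makes five lipids its primary objective and tests each at p ≤ 0.05 with no primary lipid, success rule, sidedness or adjustment. If any one favourable lipid is accepted, false benefit is about four times the rate for a single two-sided test, and still about three times (7.7%) if all correlations were 0.7. On one-sided tests the absolute risk is about double that, but so is the single-test reference. The silence on the rule is certain. The size rests on assumed correlations, SDs and sidedness; only the 12.5% bound for two-sided tests is free of the correlation assumption.

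The power figures should not be read as a floor. They depend on reading 60 as the total, on equal arms and on the number analysed, which the plan's removal of values beyond 3 SD could reduce further.

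**What to change.** In the Statistical Analysis section:

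- State that the five lipids of the primary objective are tested two-sided with Holm at family-wise 0.05, and that improvement is claimed only for lipids that are favourable and significant after adjustment.
- Make this the only rule for efficacy claims on the primary objective. Say that the whole profile improved only if all five lipids pass it, and keep no separate unadjusted all-five claim.
- Report all five group differences with 95% confidence intervals labelled as unadjusted.
- Unless it is documented that the rule was set before unblinding, label it as added after the analysis. The same condition applies to naming a single primary lipid.

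Holm is valid under any correlation, so it needs none of the values assumed here.

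**Cost.** No new participants or measurements: existing p-values are re-read and the wording of claims changes. Power for a single lipid at the first Holm step falls from the planned 90% to about 72–75% with 60 analysed, about 67–70% with about 55, or about 61–64% with 60 if Equation 1 was one-sided. The whole-profile claim is harder. Even the unadjusted all-five rule had simulated power of only 39–67% when all four measured lipids improved by 0.837 SD, and requiring all five to pass Holm cannot be easier. Some nominally significant lipids may no longer support the primary claim.

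### The safety objective rests on five serum markers, with no described collection of adverse events, so it supports a statement on liver and kidney markers but not on overall safety or tolerability

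*Combined protocol and SAP*

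**What the plan says.** Under Research Objectives, one secondary aim is to "assess the safety of the supplement by measuring serum levels of liver and kidney enzymes". The measures listed are "alanine transaminase; ALT, aspartate transaminase; AST, lactate dehydrogenase; LHD, blood urea nitrogen; BUN, and creatinine" (LHD is evidently LDH, as the Blood Analysis section prints it). The matching hypothesis is "No significant changes will be seen in anthropometric measures (waist circumference, body mass index) or liver and kidney functions biomarkers" between the groups; no margin or abnormality threshold is given.

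Blood Collection places draws at eligibility, baseline and the end of the 90 days. For participant records, Study Design says "A log was given to the participants to record their supplement intake", and food and step records are kept on days 1, 45 and 90. The dietary section has the food and activity records handed in at the final session.

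Blood pressure and heart rate come under Cardiac Measurements: "The blood pressure of each participant was taken three times, and the average was recorded". The Hypotheses section treats blood pressure as a benefit: Cardioflex participants "will have improved cardiac health, as measured by lower blood pressure, higher HRV, lower APG age".

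Statistical Analysis compares post-treatment values by analysis of covariance. It removes values more than 3 SD from the mean and recalculates.

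**The concern.** The word safety in the objective covers more than five serum markers can show. Gastrointestinal upset, dizziness, allergic reactions and intercurrent illness need not move ALT, AST, LDH, BUN or creatinine, and no described record asks about them.

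This matters on the trial's own terms. Study Design gives the lack of evidence on both effectiveness and safety as a reason for the trial, and it stresses blinding and causality. A blinded comparison of events between arms is safety evidence that this design is well placed to give, and none is planned.

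Two features of the analysis add to the problem. The 3 SD rule can delete an extreme liver value or a very low blood pressure, which are the values of most interest for safety. And a participant who stops because of intolerance and misses day 90 contributes no final marker, and no described procedure records why that person stopped.

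**Working it through.** The plan states no safety figure, so there is none to reproduce. The check is a comparison of sections, followed by arithmetic on how much safety information a trial of this size can hold.

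**1. Objective against procedures**

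| Safety information | Where the document provides for it |
|---|---|
| ALT, AST, LDH, BUN, creatinine | Objectives; Blood Analysis (assays); Blood Collection (draws) |
| Symptoms or adverse events | Not described in the available sections |
| Reasons for stopping | Not described in the available sections |
| Safety contact between baseline and day 90 | Not described; day 45 has food and step records only |
| Blood pressure, heart rate | Measured at assessment sessions, as cardiac outcomes |
| Table of events by arm | Not described in Statistical Analysis |

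**2. What collected events could show**

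Inputs: 69 starters (Sample Size section). Assuming 1:1 allocation, which is not stated, that is about 34 per arm. Expected attrition is 20%, so if exposure is incomplete the effective number could be about 34 × 0.8 = 27.

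- Chance of at least one case in the active arm at true incidence p: 1 − (1 − p)^n. With n = 34: 82.5% at p = 5%, 49.7% at 2%, 28.9% at 1%. With n = 27: 75.0%, 42.0%, 23.8%. The incidences are assumptions; the documents give none.
- No events in n participants, one-sided 95% upper bound: 1 − 0.05^(1/n). With n = 34 this is 8.4%; with n = 27 it is 10.5%.
- Formal comparison, two-sided Fisher test, 34 per arm: 5 v 0 events gives p = 0.053 and 6 v 0 gives p = 0.025, so at least 6 v 0 is needed. If the true rates were 10% v 0%, power is P(X ≥ 6) for X ~ Bin(34, 0.10), about 12%. For 10% v 3% it is about 5%.

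A table by arm would therefore be descriptive. It would show common problems but could not establish a difference.

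**3. What the markers can show**

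- 95% confidence interval half-width for a mean difference, before baseline adjustment: 1.96 × √(2/34) = 0.48 SD.
- Standardized difference detectable with 80% power: (1.96 + 0.84) × √(2/34) = 0.68.

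Baseline adjustment would narrow these by a factor √(1 − r²), where r is the correlation between baseline and final values; r is not given. Without a margin, a non-significant result is weak evidence of no effect, even for the markers measured.

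**4. Can the 3 SD rule bite at this size?**

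The largest standardized value that one observation can take in a sample of n is (n − 1)/√n. For n = 34 this is 33/5.83 = 5.66, above 3. One participant with a grossly abnormal value could therefore be removed from the safety comparison.

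**The case against.** The strongest reply is that the objective defines its own method. It promises safety by way of liver and kidney markers, the hypothesis is confined to them, and the draws and assays are in place. That is correct. A reader might infer that the objective cannot be met, but in its narrow marker form it can. What stands is that the word safety is broader than the measurements.

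A reader might also infer that the documents expect this product to lower blood pressure within 4 weeks and leave that unmonitored. They do not say so. The statement that "daily supplementation of CoQ10 can cause significant antihypertensive effects in as little as 4 weeks of treatment" is background on one ingredient. The trial's own hypothesis has no 4-week time point and treats lower blood pressure as a benefit. Blood pressure is also measured, so a mean fall at the end would be seen and individual low readings can be extracted.

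A third tempting step is to contrast a near-certain sighting of a 10% event (1 − 0.9^34 = 97%) with 0% under the plan. That rests on a rate with no source, on 1:1 allocation and on full exposure, and it says nothing about the comparison between arms. Nor is capture necessarily zero. The intake log and returned stick packs could show that someone stopped, though not why, and spontaneous reports may exist.

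Two limits remain. The opening part of the document and the consent pages could not be checked, so adverse-event reporting described there cannot be excluded. And the text is in the past tense, with 69 participants already started, so new collection may no longer be possible. These limit the remedy; they do not change what the described measurements can support.

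**Conclusion.** The point holds in this form: the plan supports a statement about mean ALT, AST, LDH, BUN and creatinine at day 90, and not a conclusion on the overall safety or tolerability of Cardioflex. The primary lipid result is unaffected.

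The gap is one of kind more than of power. Even with full collection, about 34 per arm could not exclude an event rate below 8.4% from zero events, and would have about 12% power for 10% v 0%. What is lost is a descriptive, blinded account of events by arm.

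The conclusion assumes that the unavailable pages contain no adverse-event procedure. The figures assume 1:1 allocation of the 69 starters, and the detection and power figures also assume the illustrative event rates.

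**What to change.** **If data collection is still possible:** add a symptoms and illness column to the existing intake log and one open question on adverse events at the final session. Tabulate by arm the participants with any event and those with an event leading to stopping. State that the table is descriptive.

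**If collection is over:** reword the objective and conclusion to cover liver and kidney serum markers at day 90 only, and report by arm any events and withdrawal reasons that were recorded.

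**In either case:** list by arm the individual extreme safety-marker values and the lowest individual blood pressures before any 3 SD removal. Give the marker differences with confidence intervals, so that non-significance is not read as proof of no effect.

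**Cost:** for the first route, one log column, one question and one table, with some non-specific reports to be expected in both arms. For the second, wording and one table from records already held. The listing of individual values uses data already planned.
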